6.2 Analysis of study repeaters

We will perform an analysis similar to that described in Section 6.1, using subjects in the RAS set who have completed at least one memory aid in their second year.

7. STATISTICAL ANALYSES FOR EXPLORATORY OBJECTIVES

In this section, we outline possible exploratory analyses of interest.

7.1 MN and NAI titers

We will examine MN and NAI titers in a fashion analogous to that described in Section 5.1 in the FAS. We will perform an analysis similar to that described in Section 7.1 in the RAS.

7.2 Persistence/durability of HAI and MN titers

We will perform analyses similar to those described in Section 5.1 in the FAS, except using information from Visit 4 as the outcome in order to assess long-term durability of HAI and MN titers.

7.3 Influenza detection

We will use a mixed model to compare the odds of symptomatic influenza, detected by PCR, during flu season between randomized treatment groups using the FAS. Further, we will evaluate whether there is evidence that baseline covariates (e.g., GVHD) predict odds of symptomatic influenza.

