**c. Pediatric Acute Lymphoblastic Leukemia (ALL) Subjects.** This single-center, randomized, double-blind, phase I safety and immunogenicity trial was conducted at Vanderbilt University, comparing HD to standard dose TIV in children 3-17 years of age with ALL. Fifty subjects were enrolled (20 in year 1 and 30 in year 2), with a mean age of 8.25 years, 62% were male, and 78% were receiving maintenance therapy. Thirty-four subjects were given HD and 16 were given standard dose. Safety data revealed no differences between the groups for total solicited systemic and local reactions; however, the standard dose group reported more fatigue and headache. No SAEs were attributed to vaccination. The immune response, measured by a  $\geq 4$ -fold rise in HAI titer, was similar for each vaccine antigen in both groups; however, descriptive data in ALL recipients comparing specific B-cell immune response to each antigen suggest better responses with HD-TIV (unpublished data, [name] laboratory, St. Jude, Memphis, TN). The main results are published in *Pediatric Blood Cancer*.

**5. Inclusion of Quadrivalent Inactivated Influenza Vaccine (QIV).** Although two influenza B lineages have been co-circulating since the 1980s, TIV contains only one B strain, which provides little-to-no protection against the alternate B-lineage strain; however, about 70% of recent B viruses have been antigenically related to the B virus component of the trivalent flu vaccines. A standard-dose QIV is currently available and provides additional protection against the second B strain while retaining non-inferior immunogenicity to the other 3 TIV strains. High dose QIV will not be available for the upcoming influenza season (*personal communication with Sanofi Pasteur*). This study will be the first to evaluate standard dose QIV and HD-TIV in this population.

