**Influenza Surveillance:** Active surveillance for influenza-like symptoms will begin when influenza season starts in each site's community. Influenza season begins in the specific community, defined as in previous trials by identification of at least 2 positive respiratory tests for influenza, with at least 10% of diagnostic tests positive during 2 consecutive weeks in the local clinical or research laboratory. Enrollment will continue during influenza season with nasal swabs obtained at all main visits during the influenza season to document the occurrence of influenza virus detection both prior to and after vaccination.

During the influenza season, the study staff will attempt to do a weekly telephone and/or electronic communication with the participants to detect and document any influenza like illness (ILI).

**If subjects meet ILI criteria (see below),** a nasal swab will be collected.

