- e. **Influenza-Like-Illness assessment.** The percentage of individuals in each group that test positive for influenza by PCR and the number of ILIs in each group during the influenza season will be compared.

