- To compare MN and NAI responses between subjects receiving HD-TIV and SD-QIV in the first year.
- To compare MN and NAI titers between treatment groups (two doses of HD-TIV vs. two doses of SD-QIV) among those enrolled for a second year, and compare them to HAI responses.
- To compare influenza virus detection during influenza season between treatment groups (two doses of HD-TIV vs. two doses of SD-QIV).
- To evaluate the correlation between HAI and baseline MN responses.

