2. GENERAL CONSIDERATIONS FOR DATA ANALYSES

2.1 Estimands of interest

All primary analyses will be intention-to-treat (ITT) in nature, maintaining fidelity to randomized group. Per-protocol analyses may be performed as a sensitivity analysis.

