8. TABLES

TABLE 1: STUDY SITES

#	Site
1	Vanderbilt University
2	Seattle Children's Hospital
3	Children's Hospital of Philadelphia (CHOP)
4	Children's Mercy Hospital
5	Cincinnati Children's Hospital
6	Nationwide Children's Hospital
7	St. Jude Children's Research Hospital
8	UCSF (University of California San Francisco) Benioff Children's Hospital
9	Baylor School of Medicine, Texas Children's Hospital

TABLE 2: DEFINITION OF ANALYSIS SETS

#	Analysis set	Description
1	All randomized (ARAS)	All participants randomized into the study, for use in by-subject listings.
2	Full (FAS)	All participants who (1) are randomized into the study and (2) have received at least 1 dose of either vaccine.
3	Safety (SAS)	All participants who (1) are randomized into the study and (2) have completed at least one memory aid.
4	Repeating (RAS)	All participants who are (1) randomized into the study and (2) received at least one vaccination as a repeater.

TABLE 3: PARAMETERS FOR MIXED MODEL OF INTEREST

#	Comparison	Visit	Comparison	Parameter	Null hypothesis	Classification
1	2 doses HD-TIV 2 doses SD-QIV	3 3	Between-group	$\exp(\beta_3)$	$H_0: \beta_3 = 0$	Primary
2	1 dose HD-TIV 1 dose SD-QIV	2 2	Between-group	$\exp(\beta_1)$	$H_0: \beta_1 = 0$	Secondary
3	1 dose SD-QIV 2 doses SD-QIV	2 3	Within SD-QIV	$\exp(\beta_2)$	$H_0: \beta_2 = 0$	Secondary
4	1 dose HD-TIV 2 doses HD-TIV	2 3	Within HD-TIV	$\exp(\beta_2 + \beta_3)$	$H_0: \beta_2 + \beta_3 = 0$	Secondary
5	1 dose HD-TIV 2 doses SD-QIV	2 3	Between-group	$\exp(\beta_2 - \beta_1)$	$H_0: \beta_2 - \beta_1 = 0$	Tertiary

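### SAP 7.3 analyses only symptomatic PCR-confirmed influenza, although the stated objective is any PCR detection and in-season visit swabs are taken whether or not the child has symptoms

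*SAP*

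**What the plan says.** The planned analysis, in SAP 7.3, is a mixed model to "compare the odds of symptomatic influenza, detected by PCR, during flu season between randomized treatment groups using the FAS". The FAS is defined in SAP Table 2 as "All participants who (1) are randomized into the study and (2) have received at least 1 dose of either vaccine".

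The objective behind it, in SAP 1.2.3, is "To compare influenza virus detection during influenza season between treatment groups (two doses of HD-TIV vs. two doses of SD-QIV". Protocol C.2.b lists PCR detection of influenza in season as a secondary objective. Protocol 17.e plans to compare "The percentage of individuals in each group that test positive for influenza by PCR", and also the number of influenza-like illnesses.

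On data collection, Protocol C.1 (Influenza Surveillance) keeps enrolment open during the season and takes swabs at all main visits in that period "to document the occurrence of influenza virus detection both prior to and after vaccination". The visit-by-visit text in Protocol section 14 repeats, for Visits 1 to 4, that the in-season swab does not depend on symptoms. Children who meet the influenza-like-illness criteria are swabbed as well.

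SAP 7.3 gives no date from which cases count, no rule for a positive Visit 1 swab, and no split by influenza type. It does not tie the word symptomatic to the protocol's illness criteria. The section opens with "In this section, we outline possible exploratory analyses of interest".

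**The concern.** The outcome in 7.3 is narrower than the objective. A child whose scheduled swab is PCR-positive without symptoms is a detection under SAP 1.2.3 and Protocol 17.e, but not an event under 7.3. No other section of the SAP picks that child up, so the scheduled swabs would be collected and then contribute only where the child happened to be symptomatic.

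Two details follow. First, once any detection is analysed, the Visit 1 swab needs a rule: it is taken on the day of dose 1, so a positive result reflects infection that neither vaccine could have prevented. Second, HD-TIV has no B/Yamagata component while SD-QIV does (Protocol 10.b). A pooled influenza result therefore compares two products and cannot be read as the effect of antigen dose.

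At stake is whether the influenza result reported from this trial matches the objective it is reported under, and whether the outcome definition is settled before unblinding.

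**Working it through.** **The passages side by side**

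| Place | Outcome | Symptoms required? |
|---|---|---|
| SAP 1.2.3 (exploratory) | influenza virus detection in season | no |
| Protocol C.2.b (secondary) | detection by PCR in season | no |
| Protocol 17.e | percentage PCR-positive, plus number of ILIs | no, for the PCR part |
| Protocol C.1 and 14 | swabs at in-season main visits | no |
| SAP 7.3 | symptomatic, PCR-detected influenza | **yes** |

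Four places agree and 7.3 differs. That comparison carries the point; the arithmetic below only gives scale.

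**The plan's own figure.** No sample size is given for influenza. The only one is for seroprotection, 40% vs 20% with 80% power (Protocol 17.a). With unpooled variance, n = (1.96 + 0.8416)² × (0.4×0.6 + 0.2×0.8) / 0.20² = 7.849 × 0.40 / 0.04 = 78.5, so 79 per arm (82 with pooled variance), against 80 stated. For dropout, 80/0.8 = 100 per arm, 200 in total. The figure reproduces but does not bear on influenza.

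**Scale of the influenza analysis (illustration).** Inputs: attack rate 10–20% (Protocol B.1, general population); relative efficacy 24.2% (Protocol B.3.c, adults of 65 and over); 100 per arm; two-sided 0.05. Neither clinical input comes from children after transplant.

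- Expected events: 100 × 0.10 to 0.20 = 10–20 in the SD-QIV arm, and × 0.758 = about 8–15 in the HD-TIV arm.
- One reclassified case is 1/20 to 1/10, or 5–10%, of the SD-QIV count.
- Power for 10% vs 7.58% is about 9%; for 20% vs 15.16% it is about 14%.

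**Effect of early cases and of the missing B lineage (illustration under assumed shares).** Let f be the share of SD-QIV cases arising before the vaccine can act, and y the B/Yamagata share of the later SD-QIV cases. Assume SD-QIV prevents 50% of B/Yamagata cases and HD-TIV none, so the ratio for those cases is 1/(1 − 0.5) = 2. Then

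RR = f + (1 − f) × [(1 − y) × 0.758 + y × 2].

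Protocol B.5 says "about 70% of recent B viruses have been antigenically related to the B virus component of the trivalent flu vaccines", which leaves about 30% in the other lineage. If influenza B is 10% or 40% of cases (assumed), y = 0.10 × 0.30 = 3% or 0.40 × 0.30 = 12%.

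| f | y | RR | Apparent relative efficacy |
|---|---|---|---|
| 0 | 0 | 0.758 | 24.2% |
| 10% | 0 | 0.782 | 21.8% |
| 30% | 0 | 0.831 | 16.9% |
| 50% | 0 | 0.879 | 12.1% |
| 0 | 3% | 0.795 | 20.5% |
| 0 | 12% | 0.907 | 9.3% |
| 30% | 3% | 0.857 | 14.3% |
| 30% | 12% | 0.935 | 6.5% |

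Early cases should fall equally in the two arms and pull the ratio toward 1. B/Yamagata cases move it against HD-TIV. The documents give neither f nor the influenza B share, so these rows show direction and rough scale only.

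**The case against.** The best defence is that little hangs on this analysis. The SAP calls it exploratory, power is low whatever the outcome definition, and symptomatic PCR-confirmed influenza is arguably the outcome of more clinical interest. All of that stands, and it is why the point is minor. It does not close the gap: a symptomatic outcome can sit beside the stated one but does not replace it.

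Several stronger readings are tempting, and the documents do not support them.

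- *The FAS needs only one dose, so the two-dose objective goes untested.* Children are randomised to two-dose regimens, and comparing everyone as assigned is a valid test of those assignments. It also fits SAP 2.1: "All primary analyses will be intention-to-treat (ITT) in nature, maintaining fidelity to randomized group" (worded for primary analyses). Counting only cases after dose 2 conditions on events after randomisation. It is a different estimand, suited to a sensitivity analysis.
- *The SAP will count infections present before vaccination.* It is silent on this. Eligibility already excludes proven influenza before enrolment, and fever or acute illness within 48 hours delays vaccination. What remains is that Visit 1 swabs go to central PCR and no result is required before dosing, so an unrecognised positive is possible.
- *Counting B/Yamagata cases is an error.* Both objectives cover influenza without restriction by type, and all-influenza is a fair comparison of the two products. Only the interpretation as a dose effect is limited.
- *Late enrolment shortens time at risk and needs an offset.* Randomisation is 1:1 and balanced within site, so time at risk should balance. An exposure offset also belongs in a rate or complementary log-log model, not in a logistic odds model.
- *No other clinical outcome is planned.* Protocol 17.e also compares ILI counts, and solicited adverse events are clinical outcomes.

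**Conclusion.** The concern holds as a mismatch between objective and analysis: 7.3 restricts to symptomatic cases an outcome that SAP 1.2.3, Protocol C.2.b and Protocol 17.e define as PCR detection, and it leaves asymptomatic detections from the scheduled swabs unanalysed. This follows from the text and needs no assumption. Its numerical size is unknown because the asymptomatic share is not given.

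The missing rule for Visit 1 positives and the missing split by type are secondary. Both rest on the SAP's silence, and their possible effect (24.2% falling to between 21.8% and 6.5% in the illustrations) depends on assumed shares and on an efficacy figure from older adults. Severity is minor. The as-randomised comparison in the FAS is sound and should stay.

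**What to change.** In SAP 7.3:

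1. Make any PCR detection of influenza after vaccination, in the FAS and as randomised, the analysis of the stated objective. Keep symptomatic PCR-positive influenza as a second outcome and define symptomatic, for example by the protocol's ILI criteria.
2. Treat a positive Visit 1 swab as a baseline finding, not an outcome. State how a later positive in the same child is counted, since Protocol B.1 notes prolonged shedding in immunosuppressed people.
3. Add a sensitivity analysis of cases from a stated lag after dose 2 (14 days, for example).
4. Where the PCR gives the type, report influenza A separately; both vaccines contain the same A strains. A split into A and B does not separate the two B lineages, and Protocol 15.f mentions no typing, so this item is conditional. State that the pooled result compares products and does not isolate dose.

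The cost is a few sentences in the SAP and slightly more analysis, using swabs and dates the protocol already collects. The sensitivity analysis will have fewer countable events. The wording should be settled before unblinding, as SAP 1.3 already requires a final SAP before the unblinded primary and secondary analyses.

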**1. Inclusion criteria**

- a. Allogeneic HSCT recipients who are 3-35 months post-transplant;
- b. 3-17 years of age, inclusive;
- c. Available for duration of study;
- d. Patients with stable GVHD for at least 4 weeks will be eligible (stable is defined as having no major increases in systemic immunosuppressive therapy for GVHD; adjustments of established medications to obtain a stable target level are acceptable and do not impact eligibility). Parent/legal guardian willing and capable of signing written informed consent;
- e. Parent/legal guardian expected to be available for entire study;
- f. Parent/legal guardian can be reached by telephone and/or electronic communication.
- g. Subjects must have a platelet count of  $\geq 30,000$  to receive the immunizations. Patients requiring platelet transfusions are eligible to enroll and must have a platelet count  $\geq 30,000$  within 72 hours prior to their immunization, or platelet count  $\geq 75,000$  without transfusion documented within 30 days for subjects <12 months post-transplant and within 90 days for subjects 12-35 months post-transplant.

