#### **ILI criteria: One of following criteria met:**

- **Fever:**  $\geq 38.3^{\circ}\text{C}$  ( $101^{\circ}\text{F}$ ); or
- **Two or more of any of the following:** respiratory symptoms (rhinorrhea, sinus congestion, post-nasal drip, shortness of breath, cough, wheezing, sputum production, sore throat, sneezing, watery eyes, ear pain, hoarseness); or systemic symptoms (myalgias and headache).

A nasal swab will be collected. If distance is an issue or if symptoms start on a weekend, subjects will be given PrimeStore MTM to take to their local pediatrician's office, or with proper instructions, home collection can be done, and arrangements will be made for specimens to be sent either to the local academic center or directly to Vanderbilt in Nashville, TN. Specimens should be collected within 7 days of onset of symptoms, ideally within 48 hours.

Note: For subjects who finish their visit 4 before the end of the flu season, influenza surveillance will continue until the end of the flu season at their site's community.

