### **Optional visits: 5-10 days after each vaccination**

- Only those subjects who volunteer, will return for a blood draw only.
- Approximately 20-40 mL of blood will be collected for B and T cells responses.
- If within the 8-10 days phone call window, this would replace the 8-10 day telephone and/or electronic communication.

Note: Data for proven clinical influenza infection will be collected during the study period and through June 30th.

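### SAP 7.3 tests covariates as predictors of influenza with no allowance for time under surveillance, so odds ratios for covariates linked to late-season entry would be biased downward

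*SAP*

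**What the plan says.** SAP 7.3 uses a mixed model to "compare the odds of symptomatic influenza, detected by PCR, during flu season between randomized treatment groups using the FAS". It then evaluates "whether there is evidence that baseline covariates (e.g., GVHD) predict odds of symptomatic influenza". The outcome is binary and the scale is odds. SAP 7.3 names no offset, person-time, entry-date term or time-to-event model. The FAS (SAP Table 2) requires randomisation and at least one dose, with no minimum period of observation. Protocol C.17.e likewise compares only percentages and counts.

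The protocol describes staggered entry:

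- **Entry.** Under Influenza Surveillance in C.1: "Enrollment will continue during influenza season with nasal swabs obtained at all main visits during the influenza season".
- **Start of weekly contact.** Same section: "Active surveillance for influenza-like symptoms will begin when influenza season starts in each site's community".
- **End.** For children who finish visit 4 before the season is over, C.14 says "influenza surveillance will continue until the end of the flu season at their site's community". The note under the optional visits in C.14 adds: "Data for proven clinical influenza infection will be collected during the study period and through June 30".

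Eligibility depends partly on clinical timing. C.4.A.1 sets a minimum of 3 months after transplant and says "Patients with stable GVHD for at least 4 weeks will be eligible". C.4.A.2 excludes recent immunoglobulin, a recent stem cell boost or delayed donor lymphocytes, and proven influenza earlier in the season.

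**The concern.** A child dosed before the local season is observed for all of it, and a child dosed at mid-season for roughly half. The model in SAP 7.3 gives both the same weight. A child with no recorded case after half a season counts as influenza-free, just like a child with no recorded case after a full one. Influenza before entry cannot be counted either, because proven disease earlier in the season excludes the child.

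This matters for covariates only if they go with entry date. The eligibility waits make that plausible for short time since transplant and for GVHD that was recently unstable. Protocol C.5.a limits children at least 12 months after transplant to 60 of 200, so most of the planned sample is in the 3-11 month range, where the 3-month rule can decide when a child enters.

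At stake is the reading of the covariate result. GVHD is the SAP's own example. A null or apparently protective GVHD coefficient could not be separated from shorter observation.

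**Working it through.** The documents give no event count, risk or power figure for this endpoint, so there is no plan figure to reproduce.

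**Does another section supply the missing term?** No. SAP 2.3 maps visits to windows and imputes missing data, but a child watched for part of a season is recorded as having no influenza, not as missing. SAP 7.3 names no covariate other than GVHD, so adjustment for entry date cannot be assumed.

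**Inputs**

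- Full-season risk p: 10% and 20%. Protocol B.1 gives this range for the general population and says HSCT recipients have higher rates. Used here as an assumption.
- Hazard: constant over the season (assumption).
- Fraction f of the season observed by late entrants, and the share entering late among children with the covariate (s1) and without it (s0): assumptions, because no entry dates are reported.

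**Formulas**

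- Risk of a late entrant: q = 1 - (1 - p)^f
- Group risks: r1 = s1·q + (1 - s1)·p and r0 = s0·q + (1 - s0)·p
- Spurious odds ratio with no true effect: [r1/(1 - r1)] / [r0/(1 - r0)]

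**Worked example: p = 10%, f = 0.5, s1 = 50%, s0 = 20%**

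- q = 1 - 0.9^0.5 = 0.0513
- r1 = 0.5×0.0513 + 0.5×0.1 = 0.0757
- r0 = 0.2×0.0513 + 0.8×0.1 = 0.0903
- Odds ratio = (0.0757/0.9243)/(0.0903/0.9097) = 0.825

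**Range for a covariate with no true effect**

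| Link to late entry | f | OR, p = 10% | OR, p = 20% |
|---|---|---|---|
| Weak: 30% vs 20% late | 0.5 | 0.94 | 0.94 |
| Partial: 50% vs 20% | 0.5 | 0.83 | 0.82 |
| Strong: 60% vs 10% | 0.25 | 0.58 | 0.56 |
| Complete: 100% vs 0% | 0.5 | 0.49 | 0.47 |
| Complete: 100% vs 0% | 0.25 | 0.24 | 0.23 |

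**A true risk factor (hazard ratio 2, f = 0.5).** With the partial link the odds ratio is 1.71 (p = 10%) or 1.76 (p = 20%), against 2.11 and 2.25 with equal observation. With the complete link it is 1.00.

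**Against sampling noise.** Take 200 children and an assumed covariate prevalence of 30% (60 vs 140), with the partial link.

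- p = 10%: SE of the log odds ratio = √[1/(60×0.0757×0.9243) + 1/(140×0.0903×0.9097)] = 0.57.
- p = 20%: the same formula with r1 = 0.1528 and r0 = 0.1811 gives 0.42.
- The bias is ln 0.825 = -0.19 and ln 0.815 = -0.20, under half a standard error in both cases.

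**Simulation** (200 children, prevalence 30%, 2,000 runs per scenario, no true effects). Logistic regression without time rejected the null covariate in 2% (partial, p = 10%), 6% (partial, p = 20%), 21% (strong, p = 20%) and 34% (complete with f = 0.5, p = 20%) of runs. The arm comparison was rejected in 4-5% of runs throughout.

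**Why a log(weeks) offset is not the repair.** It works when the weekly hazard is flat. Suppose instead that 80% of the season's risk falls in its second half (illustration). A mid-season entrant then carries 80% of the risk in 50% of the weeks, and the offset yields a spurious hazard ratio of 0.8/0.5 = 1.6 for a covariate carried only by such entrants. The bias has changed sign.

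**The case against.** The strongest reply is that the link between covariates and entry date is inferred, not shown, and that the waits are shorter than they sound. Stable GVHD is eligible at once. Only a major increase in therapy starts the 4-week clock. At an assumed 0.75% per week over 20 weeks, losing 4 weeks changes the risk from 1 - exp(-0.15) = 13.9% to 1 - exp(-0.12) = 11.3%. That is an odds ratio of about 0.79 for that child, and nearer 1 for a GVHD group that includes stable cases. The immunoglobulin wait is under 27 days, and C.14 allows vaccination on the infusion day. A child who reaches 3 months before the season loses nothing. All of this stands. It limits the likely size but does not remove the gap.

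The stakes are also low. SAP 7 calls these possible exploratory analyses, and the influenza objective in SAP 1.2.3 is the arm comparison only. That stands too and sets the severity.

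A reader might go further and infer that such covariates must look protective, or that a real risk would be reversed. The documents do not support this. A downward pull on a covariate with a true effect need not take it below 1. With a hazard ratio of 1.5, the odds ratio falls below 1 (to 0.74 or 0.73) in the extreme case where every child with the covariate sees half the season and every other child all of it. With the partial link it stays at about 1.26-1.27.

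**Conclusion.** The gap is real and minor. SAP 7.3 compares children observed for different parts of the season as if they were equally observed, and no other section corrects this. The direction follows from the text: an odds ratio for any covariate that goes with late entry is biased downward. The size does not follow from the text. It rests on an assumed constant hazard and assumed entry patterns. About 0.94 to 0.83 for a null covariate covers weak to partial links at mid-season, and 0.23 needs a complete link with only a quarter of the season observed.

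A reader might also infer that the vaccine comparison is affected. It is not: entry precedes allocation, so late entry is balanced between arms in expectation, and the simulated rejection rate stayed at 4-5%.

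This is a cheap improvement to an exploratory analysis, worth making before the covariate results are interpreted.

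**What to change.** For the covariate analysis in SAP 7.3, replace the odds model with a model for time to first symptomatic PCR-confirmed influenza:

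- **Time scale:** calendar time, so that each case is compared with children under observation on the same date and the shape of the epidemic drops out.
- **Delayed entry:** at the later of first dose and local season start.
- **Stratification:** by season, and by site where event numbers allow.
- **Censoring:** at withdrawal, death or a stated season-end date. C.1 and C.14 define how the season begins but not how it ends, so a date must be fixed. June 30, which C.14 already uses for collecting proven influenza, is one option.
- **Repeaters:** state whether a second season counts.

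Do not rely on a log(weeks) offset alone. The arm comparison may stay on the odds scale.

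The cost is SAP wording, a season-end definition and derived entry and exit dates. No visit or sample changes. The covariate effect becomes a hazard ratio. Precision will be limited: the partial-link scenario above implies only about 17 events (60×0.0757 + 140×0.0903) to 35 events (60×0.1528 + 140×0.1811) among 200 children.
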